Appendix A: ECOG/KPS Scale

ECOG Performance Status Scale		Karnofsky Performance Scale	
Grade	Descriptions	Percent	Description
0	Normal activity. Fully active, able to carry on all pre-disease performance without restriction.	100	Normal, no complaints, no evidence of disease.
		90	Able to carry on normal activity; minor signs or symptoms of disease.
1	Symptoms, but ambulatory. Restricted in physically strenuous activity, but ambulatory and able to carry out work of a light or sedentary nature (e.g., light housework, office work).	80	Normal activity with effort; some signs or symptoms of disease.
		70	Cares for self, unable to carry on normal activity or to do active work.
2	In bed <50% of the time. Ambulatory and capable of all self-care, but unable to carry out any work activities. Up and about more than 50% of waking hours.	60	Requires occasional assistance, but is able to care for most of his/her needs.
		50	Requires considerable assistance and frequent medical care.
3	In bed >50% of the time. Capable of only limited self-care, confined to bed or chair more than 50% of waking hours.	40	Disabled, requires special care and assistance.
		30	Severely disabled, hospitalization indicated. Death not imminent.
4	100% bedridden. Completely disabled. Cannot carry on any self-care. Totally confined to bed or chair.	20	Very sick, hospitalization indicated. Death not imminent.
		10	Moribund, fatal processes progressing rapidly.
5	Dead.	0	Dead.

Appendix B: IMWG Response Criteria

Serum and urine M-protein estimates will be performed every 4 weeks; except for assessment of CR, patients with measurable disease restricted to the SPEP (or UPEP) will need to be followed only by SPEP (or UPEP). Responses will be assessed according to the criteria of the International Myeloma Working Group⁶¹, and characterized as follows:

Response Category	Response Criteria ^a
SCR	CR as defined below plus 
 • Normal FLC ration and • Absence of clonal cells in bone marrow^b by immunohistochemistry or immunofluorescence^c
CR	Negative immunofixation on the serum and urine and disappearance of any soft tissue plasmacytomas and $\leq 5\%$ plasma cells in bone marrow ^b
VGPR	Serum and urine M-protein detectable by immunofixation but not on electrophoresis or 90% or greater reduction in serum M-protein plus urine M-protein level < 100 mg per 24 hours
PR	$\geq 50\%$ reduction of serum M-Protein and reduction in 24 hour urinary M-protein by $\geq 90\%$ or to < 200 mg per 24 hours If the serum and urine M-protein are unmeasurable ^d a $\geq 50\%$ decrease in the difference between involved and uninvolved FLC levels is required in place of the M-protein criteria If serum and urine M-protein are unmeasurable, and the serum free light assay is also unmeasurable, $\geq 50\%$ reduction in plasma cells is required in place of M-protein provided baseline bone marrow plasma cell percentage was $\geq 30\%$ In addition to the above, if present at baseline a $\geq 50\%$ reduction in the size of soft tissue plasmacytomas is also required
SD^e	Not meeting criteria for CR, VGPR, PR, or progressive disease
Relapse Category^f	Relapse Criteria
Progressive disease	Requires only one of the following: Increase of $\geq 25\%$ from baseline in: 
 • Serum M-component and/or (the absolute increase must be ≥ 0.5 g/dl)^g • Urine M-component and/or (the absolute increase must be ≥ 200 mg/24 hours) • In patients without measurable serum and urine M-protein levels the difference between involved and

	
uninvolved FLC levels, the absolute increase must be $> 10 \text{ mg/dl}$.
 
 • Bone marrow plasma cell percentage, the absolute % must be $\ge 10\%$^h. • Definite development of new bone lesions or soft tissue plasmacytomas increase in the size of existing bone lesions or soft tissue plasmacytomas. • Development of hypercalcemia (corrected serum calcium $> 11.5 \text{ mg/dl}$ or 2.65 mmol/l) that can be attributed solely to the plasma cell proliferative disorder.
Clinical relapse (Not used for TTP or PFS)	Clinical relapse requires one or more of: 
 • Development of new soft tissue plasmacytoma or bone lesions • Definite increase in the size of existing plasmacytomas or bone lesions. A definite increase is defined as a 50% (and at least 1 cm) increase as measured serially by the sum of the products of the cross-diameters of the measurable lesion • Hypercalcemia ($> 11.5 \text{ mg/dl}$ [2.65 mmol/l]) • Decrease in hemoglobin of $\ge 2 \text{ g/dl}$ (1.25 mmol/l) • Rise in serum creatinine by 2 mg/dl or more ($177 \mu\text{mol/l}$ or more)
Relapse from CR ⁱ	Any one or more of the following: 
 • Reappearance of serum or urine M-protein by immunofixation or electrophoresis • Development of $\ge 5\%$ plasma cells in the bone marrow^j • Appearance of any other sign or progression

a. All response categories require two consecutive assessments made at anytime before the institution of any new therapy; all categories also require no known evidence of progressive or new bone lesions if radiographic studies were performed. Radiographic studies are not required to satisfy these response criteria.

b. Confirmation with repeat biopsy not necessary.

c. Presence/absence of clonal cells is based upon the κ/λ ratio by immunohistochemistry and/or immunofluorescence requires a minimum of 100 plasma cells for analysis. An abnormal ration reflecting presence of an abnormal clone is κ/λ of $> 4:1$ or $< 1:2$.

d. Applicable only to patients who have 'measurable' disease defined by at least one of the following three measurements: Serum M-protein $\ge 1 \text{ g/dl}$, Urine M-protein $\ge 200 \text{ mg/24hour}$, Serum FLC assay involved FLC level $\ge 10 \text{ mg/dl}$ provided serum FLC ration is abnormal.

e. Not recommended for use as an indicator of response; stability of disease is best described by providing the time to progression estimates).

f. All relapse categories require two consecutive assessments made at anytime before classification as relapse or disease progression and/or the institution of any new therapy.

g. For progressive disease, serum M-component increases of $\ge 1 \text{ gm/dl}$ are sufficient to define relapse if starting M-component is $\ge 5 \text{ g/dl}$.

h. Relapse from CR has the 5% cutoff versus 10% for other categories or relapse.

i. To only be used if the end point studied is disease free survival. For purposes of calculating time to progression and progression-free survival, CR patients should also be evaluated using criteria listed above for progressive disease.

j. Relapse from CR has the 5% cutoff versus 10% for other categories of relapse.

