6.3 Clinical outcome definitions

Time to progression: TTP will be defined as the time from start of treatment until the date he or she has progression or dies. Any subject who has received study treatment but has neither progressed nor died will be censored on the date of his or her last tumor assessment. A subject who has not received study treatment and who has neither progressed nor died will be censored on the day he or she was enrolled.

Progression Free Survival: PFS will be defined as the time from study entry until disease progression or death at trial closure for the per protocol population. Patients who withdraw from the trial prior to disease progression and who are either lost to follow-up, die or who begin alternative treatments prior to progression, will have their data censored as of the date considered to be lost to follow-up, date of death, or the first day of alternative therapy.

Time to Response: A subject's time to response is defined as the time from first dose of study therapy until measurement criteria are first met for [VG]PR or CR or SD (whichever status is recorded first). Time to response is computed only for subjects whose best response is [VG]PR or CR.

Duration of Overall Response: The duration of overall response will be computed for subjects whose best response is either [VG]PR or CR or SD. It will be measured from the time measurement criteria are first met for complete response or partial response (whichever status is recorded first) until the first date of progressive disease or death. Subjects who neither progress nor die will be censored on the date of their last tumor assessment.

Overall Survival: A subject's survival time will be defined as the time from start of treatment to the date of his or her death. If the subject has not died, survival will be censored on last date the subject was known to be alive.

Response Rate: The tumor response rate will be defined as the total number of subjects whose best response is PR or VGPR or CR or SD, divided by the number of per protocol patients.

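### Appendix B measures progression as a 25% rise from baseline, not from the lowest value reached, so any patient whose M-protein fell must pass the pre-treatment level before that route counts, which dates TTP, PFS and response-duration events late

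*Combined protocol and SAP*

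**What the plan says.** The progressive-disease row of Appendix B opens "Requires only one of the following: Increase of $\geq 25\%$ from baseline in" and then lists four laboratory routes, each with an absolute condition. The serum line is "Serum M-component and/or (the absolute increase must be ≥ 0.5 g/dl") and the urine line is "Urine M-component and/or (the absolute increase must be ≥ 200 mg/24 hours"). Free light chain difference and marrow plasma cells follow. New or enlarging bone lesions or plasmacytomas, and hypercalcemia, also count as progression.

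In this table baseline means the pre-treatment value. The partial-response row uses it that way for marrow ("is required in place of M-protein provided baseline bone marrow plasma cell percentage was" at least 30%). Footnote g, on rises of 1 g/dl or more in patients with a high M-component, is also tied to the entry value: such rises "are sufficient to define relapse if starting M-component is" 5 g/dl or more.

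The other relapse rows do not feed these endpoints. Clinical relapse is labelled as not used for TTP or PFS. Footnote i confines relapse from CR to disease-free survival, which is not an endpoint here, and adds: "For purposes of calculating time to progression and progression-free survival, CR patients should also be evaluated using criteria listed above for progressive disease".

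Section 6.3 ends TTP and PFS at progression or death, and runs duration of response "until the first date of progressive disease or death". It censors PFS when a patient who has withdrawn before progression starts alternative treatment. TTP is a secondary endpoint in section 2.4. PFS is called secondary in section 2.1 and exploratory in section 6.1.2, where it is also one of the factors that settle a result of 10 or 11 responses in 29.

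**The concern.** For a patient whose M-protein never falls, a rise from baseline and a rise from the lowest value are the same thing. For anyone whose M-protein falls, they are not. A patient who goes from 3.0 to 0.3 g/dl and back to 3.0 has lost the whole response, yet by the M-protein route has not progressed. A CR patient is in the same position, because footnote i applies the same rule.

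The routes that could intervene are only partly scheduled. Section 5.8.6 lists a skeletal survey at screening and end of treatment, and its footnote c makes a survey after baseline optional, at evidence of progression. Imaging can therefore wait for a signal that the M-protein rule delays. Under footnote k, follow-up marrow is for non-secretory disease.

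At stake is how durable responses appear. There is one arm, so no concurrent control carries the same delay.

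**Working it through.** The plan states no figure that depends on the reference value, so the check compares progression thresholds under the two readings.

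**Inputs from the documents.** Relative rise 25% and minimum serum rise 0.5 g/dl (Appendix B); minimum urine rise 200 mg/24 h (Appendix B); serum falls of at least 50% for PR and 90% for VGPR (Appendix B); lowest serum M-protein admitted as measurable, 0.5 g/dl (section 3.1); footnote g applies from 5 g/dl.

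**Assumptions.** Example baselines of 0.5 to 4.9 g/dl (just below footnote g), exponential regrowth, and doubling times of 1 to 4 months.

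**Formulas.** With reference value R, the serum threshold is T(R) = max(1.25R, R + 0.5). For baseline B and lowest value L, the delay in doublings is log2[T(B)/T(L)]. T(B) is above B for every B.

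**Example, B = 3.0 g/dl.** T(3.0) = max(3.75, 3.5) = 3.75.
- 50% fall: T(1.5) = max(1.875, 2.0) = 2.0; delay log2(3.75/2.0) = 0.91.
- 90% fall: T(0.3) = max(0.375, 0.8) = 0.8; delay log2(3.75/0.8) = 2.23.
- 25% fall (stable disease): T(2.25) = max(2.81, 2.75) = 2.81; delay log2(3.75/2.81) = 0.42.
- No fall: delay 0.

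| Baseline (g/dl) | Fall | T from baseline | T from lowest | Delay (doublings) |
|---|---|---|---|---|
| 0.5 | 50% | 1.0 | 0.75 | 0.42 |
| 0.5 | 90% | 1.0 | 0.55 | 0.86 |
| 1.0 | 50% | 1.5 | 1.0 | 0.58 |
| 1.0 | 90% | 1.5 | 0.6 | 1.32 |
| 3.0 | 50% | 3.75 | 2.0 | 0.91 |
| 3.0 | 90% | 3.75 | 0.8 | 2.23 |
| 4.9 | 50% | 6.125 | 3.06 | 1.00 |
| 4.9 | 90% | 6.125 | 0.99 | 2.63 |

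**In months.** After a 50% fall: 0.42 × 1 to 1.00 × 4, about 0.4 to 4.0 months. After a 90% fall: 0.86 × 1 to 2.63 × 4, about 0.9 to 10.5 months. These are delays on the M-protein route for one patient who is followed until the higher threshold is reached.

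**Urine.** Baseline 1000 mg/24 h and a 90% fall to 100: thresholds max(1250, 1200) = 1250 and max(125, 300) = 300; delay log2(1250/300) = 2.06 doublings.

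**Footnote g.** It does not say from which value the 1 g/dl rise is counted. If it is counted from the same reference as the 25% rise, baselines of 5, 6 and 8 g/dl give delays of 0.94, 0.90 and 0.85 (50% fall) and 2.58, 2.67 and 2.79 (90% fall), so the pattern continues.

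**Reach into the phase II decision.** With n = 29, P(at most 9) is 0.834 at a response rate of 25% and 0.031 at 50%; P(at least 12) is 0.039 and 0.868. These agree with the stated eta of 0.83, errors of 4% and 3%, and pi of 0.87, and none depends on the progression rule. The 10-or-11 zone has probability 1 − 0.834 − 0.039 = 0.127 at 25% and 1 − 0.031 − 0.868 = 0.101 at 50%.

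**The case against.** The strongest reply has four parts.

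1. **Other events intervene.** Lesions, hypercalcemia and death all end TTP and response duration. Calcium is checked every two weeks and then monthly (section 5.8.6, footnote e), and CT is required where a plasmacytoma is the only measurable disease. Patients may also stop treatment by their own or the physician's decision, and PFS is then censored at new therapy. This stands against any estimate in months. It does not remove the problem, since an event that turns into a censored observation is also lost.
2. **The endpoints are minor.** PFS is exploratory in section 6.1.2, response duration is not listed in sections 2.3 or 2.4, and no test is set for TTP or PFS. This stands, and it limits the priority.
3. **The text may be unsettled, or may follow the cited criteria.** Footnote h attaches a 5% marrow cutoff for relapse from CR to the progressive-disease row. With a pre-treatment reference plus 25%, that cutoff could bind only if baseline marrow were below 5/1.25 = 4%, so the footnote fits the row poorly. The cited criteria are not available here. Whatever the origin of the wording, the rule as printed works as shown.
4. **Changing only the analysis creates two definitions of progression.** Progression also triggers withdrawal (sections 4.4, 5.7 and 10.7). This stands, and the fix must deal with it.

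A reader might infer that only responders are affected. Appendix B does not support that: stable disease with a fall under 50% is affected too. A reader might also set the delays beside the median TTP of about 11 months in Table 1-1 and conclude that the trial's median is inflated by a similar number of months. The documents give no baselines, regrowth rates or event mix from which to calculate that.

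**Conclusion.** The point holds as a defect in the endpoint definition. As written, a patient whose M-protein fell must exceed the pre-treatment level before the M-protein route records progression, and no other section corrects this. The direction is certain for each patient: the progression date is unchanged or later, or in PFS the event may be replaced by censoring at new therapy. TTP and duration of response are lengthened accordingly.

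The size is not computable from the documents. The illustration of 0.42 to 1.00 doublings after a 50% fall and 0.86 to 2.63 after a 90% fall rests on assumed baselines and exponential regrowth; the months rest further on assumed doubling times. It ignores earlier lesions, hypercalcemia, death and censoring.

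It would go too far to say that the phase II conclusion is compromised. The primary response rate after 4 cycles and the 29-patient rule are essentially untouched, and PFS bears on the decision only at 10 or 11 responses, as one factor among several. The change should be made, but the primary analysis does not hinge on it.

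**What to change.** For the TTP, PFS and duration-of-response analyses, state in Appendix B and section 6.3 that the 25% rise and the stated absolute minimum increases are measured from the lowest value recorded on study, or from baseline if no value was lower. Align footnotes g, h and i with that reference, including the value from which footnote g's 1 g/dl rise is counted. Report the from-baseline version as a sensitivity analysis.

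Because progression also triggers withdrawal, the sponsor must state which reference applies there and reconcile Appendix B with sections 4.4, 5.7 and 10.7. That choice is the sponsor's.

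The cost is a few sentences and no new on-treatment measurement, since Appendix B already calls for M-protein every 4 weeks. The downsides are that TTP, PFS and response duration become shorter, that the analysis definition departs from the table's present wording, and that analysis and treatment may use different definitions of progression unless the sponsor aligns them.

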4.4 Duration of Treatment

Patient can continue study treatment at the treating physician's discretion. Patients achieving at least a stable disease can continue treatment until one of the following is reached:

- Progression of disease
- Death
- Unacceptable toxicity
- Patient decision
- Treatment delay greater than 4 weeks.

Overall response will be assessed after 4, 8, and 12 cycles. If disease progression is observed at the end of Cycle 4 evaluation, all study therapy will be discontinued. In addition, study therapy will be discontinued at the time of disease progression as noted above. Otherwise patient can continue treatment until one of the above endpoints is reached.

Following the 30-day post-treatment follow-up assessment, additional evaluations will occur once per month (unless subject discontinued due to progression) until the earliest of the following events:

- Disease progression,
- The time of initiation of new therapy,
- Death or study completion.

Study completion is defined as 30 days after the last subject remaining on study medication discontinues study medication.

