5.7 Patient Withdrawal

A patient should be removed from the study whenever it is necessary to safeguard his/her welfare. Occurrence of a significant adverse event or laboratory abnormalities unexpected for these patients may also necessitate discontinuation from the study. Additional reasons for removing a patient from the study are:

- Patients who participate in another investigational drug trial
- Patients' non-compliance with the protocol that can negatively affect the treatment effect
- Patients who express a desire to withdraw from the study (the patient has the right to withdraw for any reason without prejudice)
- Evidence of progressive disease would require withdrawal of the patient from the study.
- Any other reasons deemed by the principal investigator and treating physician.
- Patients who must discontinue use of either CT-011 or lenalidomide

The reason for any patient withdrawal from the study should be recorded on the case report form (CRF) and the occurrence should be reported to the principal investigator by email. These patients who withdraw from the study in the phase II portion of the trial will not be replaced. When a patient is removed from the study, he/she will receive treatment according to the standard of care (SOC) in the medical center and will be followed-up according to the study schedule whenever possible.

A patient who is removed from the study by the investigator due to an adverse event (AE) or serious adverse event (SAE) will be followed until resolution of the toxicity to Grade 1 or baseline. All the tests that are required to assess the patient condition will be made as frequent as necessary until the AE or SAE has been resolved. Samples that have already been obtained will be processed.

A patient who withdraws consent before starting the study will not be followed up.

A patient who is removed from the study by the investigator since he/she did not keep the appointments will be hard to follow given the circumstances. The extreme situation of this occurrence is a patient who is defined as "lost to follow-up". Attempts to follow up on the subject will be made as long as the consent has not been withdrawn by the subject. Samples that have already been obtained will be processed.

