- e. CBC d/p will be monitored biweekly in cycles 1 to 4, then monthly thereafter. Chemistry tests, including electrolytes, glucose and serum creatinine, should be performed every 2 weeks during the first 2 months of therapy and once a month thereafter. Serum electrolyte monitoring should include potassium, magnesium and calcium. PTT, INR and TSH will be checked every 2 months.
- f. CBC/d/p should also be checked on day 17 of a cycle where lenalidomide's dose has been escalated.
- g. Beta 2 microglobulin will be done after every 2 cycles and at evidence of progression of disease.
- h. Baseline and periodic ECGs should be performed during treatment as indicated in the flow chart. In patients who have ECG abnormalities, ECGs should be performed more routinely as clinically indicated. ECGs post-baseline should be performed as indicated
- i. Myeloma monoclonal protein assessments (Serum protein electrophoresis & immunofixation, immunoglobulin levels, serum free light chain assay) will be performed on day 3 of each cycle (when patients come in for CT-011 infusion) as well as off study.
- j. 24hr urine monoclonal protein assessment (Urine protein electrophoresis & immunofixation) will be performed at screening and as required for response assessment.
- k. Unilateral bone marrow (BM) biopsy will be done at baseline and at end of 4th cycle and evidence of progression for patients with non secretory multiple myeloma
- l. Lenalidomide must be prescribed through and in compliance with Celgene's RevAssist® program. Prescriptions must be filled within 7 days. Any unused lenalidomide should be returned to the patient for disposition in accordance with the RevAssist® program.
- m. T-cell, NK-cell, and CD14 correlates will be collected prior to CT-011 dosing on C1D3, C1D4, C1D6, C1D10, C1D17 and then on Day 3 of all subsequent cycles. T-cell correlates only will also be collected at 1, 3, and 6 months after discontinuation of protocol therapy.
- n. Samples for CT-011 PK determination will be collected in cycle 1 prior to CT-011 infusion, immediately at the end of the infusion, 1 hour after end of infusion, approximately 24(C1D4), 72(C1D6), 168 (C1D10) & 336 (C1D17) hrs – and just prior to next (cycle 2) infusion. Off-study correlates should be obtained at the time the patient is removed from protocol for any reason.

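### Appendix B gives the hypercalcemia limit for progressive disease as two values that do not convert into each other (11.5 mg/dl and 2.65 mmol/l), so a narrow band of calcium results can be classed either way

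*Combined protocol and SAP*

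**What the plan says.** The progressive disease row of Appendix B opens with "Requires only one of the following", so each item in it is sufficient alone. One item is hypercalcemia, defined as "corrected serum calcium $> 11.5 \text{ mg/dl}$ or 2.65 mmol/l", with the further condition on its cause that completes the item: "or 2.65 mmol/l) that can be attributed solely to the plasma cell proliferative disorder".

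The clinical relapse row repeats the same two figures, this time with the mmol/l value in square brackets after the mg/dl value. That row is headed "Clinical relapse (Not used for TTP or PFS".

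Footnote f adds a confirmation rule: "All relapse categories require two consecutive assessments made at anytime before classification as relapse or disease progression".

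Section 4.4 states the consequence for treatment: "study therapy will be discontinued at the time of disease progression as noted above". Section 5.7 adds: "Evidence of progressive disease would require withdrawal of the patient from the study". Section 10.7 also lists progression among the reasons for removal from therapy. Section 6.3 makes progression an event in both TTP and PFS.

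Calcium is measured on study. Footnote e of Section 5.8.6 says "Serum electrolyte monitoring should include potassium, magnesium and calcium", within chemistry done every 2 weeks for the first 2 months and monthly thereafter. No section gives the unit for calcium or says which of the two figures governs.

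**The concern.** A threshold printed in two units should be one level. If the two figures differ, results that fall between them satisfy the criterion under one figure and fail it under the other, and the protocol gives no rule for choosing.

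This matters more here than it would in background text, because Appendix B is the working definition of progression. A single confirmed criterion ends study therapy and supplies the event date for TTP, a secondary endpoint in Section 2.4, and for PFS. Section 6.1.2 also names PFS among the factors to be weighed if the phase II result is inconclusive (10 or 11 responses in 29 patients).

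**Working it through.** **Inputs.** From Appendix B: 11.5 mg/dl and 2.65 mmol/l for calcium; 2 mg/dl and 177 µmol/l for creatinine; 2 g/dl and 1.25 mmol/l for hemoglobin. Molar masses are not in the documents and are taken as physical constants: calcium 40.078 g/mol (range tried 40.0 to 40.1), creatinine 113.12 g/mol, hemoglobin monomer 16,114 g/mol.

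**Formula.** mmol/l = (mg/dl × 10) / molar mass in g/mol.

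**The stated calcium pair does not reproduce.**
- 11.5 mg/dl: 115 / 40.078 = 2.87 mmol/l (2.868 to 2.875 over the range tried), against 2.65 stated.
- 2.65 mmol/l: 2.65 × 40.078 / 10 = 10.62 mg/dl (10.60 to 10.63), against 11.5 stated.
- Gap: 11.5 − 10.62 = 0.88 mg/dl; 2.87 − 2.65 = 0.22 mmol/l; 2.869 / 2.65 − 1 = 8.3%.

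**Could it be rounding?** The pair would agree only at a molar mass of 115 / 2.65 = 43.4 g/mol. Rounding does not explain it.

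**Do the neighbouring pairs convert?**
- Creatinine: 20 mg/l / 113.12 g/mol = 176.8 µmol/l; stated 177.
- Hemoglobin: 20 g/l / 16,114 g/mol = 1.24 mmol/l; stated 1.25. This agrees on the monomer basis only.

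Of the three pairs, only calcium fails. It appears twice with the same figures, so a PDF reading error is unlikely.

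**What the mismatch does.** Take a corrected calcium of 11.0 mg/dl, which is 110 / 40.078 = 2.74 mmol/l.
- If the two figures are alternatives, 2.74 exceeds 2.65 and the criterion is met. The lower figure then governs every patient, whatever unit the laboratory reports.
- If the mmol/l figure is only meant to restate the mg/dl figure, 11.0 does not exceed 11.5 and the criterion is not met.

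The same split holds for any value above 10.62 and up to 11.5 mg/dl.

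**Conditions for a classification to turn on this.** All must hold: corrected calcium in that band; two consecutive assessments (footnote f); attribution solely to the plasma cell disorder; no other progression criterion met. The documents give no figure for how many patients would satisfy these conditions, so none is computed.

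**The case against.** The strongest reply is that the practical effect may be nil. The protocol's other chemistry limits, such as bilirubin and creatinine in Section 3.1, are in mg/dL only, and SI values appear beside them only in Appendix B. The square brackets in the clinical relapse row suggest that 2.65 mmol/l was meant as a restatement of the mg/dl figure. On that view sites would work in mg/dl and the mmol/l figure would never be used. This is plausible and limits the point. It does not remove it: the calcium unit is not fixed anywhere, and the progressive disease row, which drives treatment and endpoints, joins the figures with a word that literally admits either.

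A second reply is that the table presents itself as the cited international response criteria (reference 61), so the mismatch may have been carried over. The documents do not settle that. Whatever its origin, Appendix B is the text the sites apply.

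Two stronger readings are tempting and should not be drawn:
- *That patients at different sites will be classified differently according to the unit reported.* Nothing in the documents shows a site reporting calcium in mmol/l. The ambiguity lies in how the row is read.
- *That the mismatch changes the phase II response count.* No response category in Appendix B mentions calcium; footnote a adds only that there be no known progressive or new bone lesions. Stable disease is defined partly by the absence of progression, but the decision rule in Section 6.1.2 counts partial and complete responses. An early stop could in principle cost a patient a later response, but no such effect on the cut-offs (at most 9, 10 or 11, at least 12 of 29) is shown.

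It is also fair that the clinical relapse row does not feed TTP or PFS, and that Section 6.1.2 calls the PFS analysis exploratory.

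**Conclusion.** The point holds as an internal contradiction in an operative definition: one criterion for progression carries two thresholds about 0.9 mg/dl (8%) apart, with nothing to say which governs. The only outside input is the molar mass of calcium, and the result is insensitive to it over 40.0 to 40.1 g/mol.

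The consequence is narrow. It reaches stopping of study therapy and the TTP and PFS events, through the progressive disease row alone, for patients who meet all the conditions listed in the working. That number is not given and is probably small. This is a minor correction and does not undermine the primary phase II analysis. It is no judgement on which level is the right one.

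**What to change.** Check both figures against the cited response criteria and reconcile them. State one governing corrected-calcium value and its unit in the progressive disease row and in the clinical relapse row, and either convert the other figure correctly or delete it. The choice of level belongs to the investigators and the cited criteria.

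The cost is one corrected figure in each of two rows of an appendix, which can go into the next amendment. If any patient has already had corrected calcium between 10.6 and 11.5 mg/dl on study, a short listing would show whether any recorded classification turned on the discrepancy.
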